4.2.1.2 Secondary

- The association of plasma concentrations (C_{max} and C_{min}) and exposure (AUC) on haematopoiesis (both short⁺ and longer-term[†] measures)
- The kinetics of recovery of haematopoiesis for a given dose and for a given duration of dosing

4.2.1.3 Exploratory^φ

- The impact of therapy on disease burden as measured by malignant-cell specific nucleic markers (DNA or mRNA)^{*}
- The effect of treatment on the immunophenotype of leukaemic and dysplastic cells^{**}
- The effect of treatment on cytokine profiles^{***}
- The relationship between genetic and cytogenetic aberrations in leukaemic cells on pharmacodynamic response
- The association of conventional clinical responses^{****} with molecular assessments of response

⁺Short term measures may include reticulocyte counts, absolute neutrophil counts (ANC), platelet volume.

[†]Longer-term measures may include return of counts to baseline or better.

^φSome or all may be analysed time and cost permitting.

^{*}Nucleic markers include tumour-specific transcripts and DNA mutations detected by sequencing.

^{**}Immunophenotyping by fluorescence-activated cell sorting or flow cytometry (FACS; FC).

^{***}Serum cytokine quantification.

^{****}Conventional clinical response parameters may comprise: CBC including platelets, red and white blood cell (RBC and WBC) and leukaemic blast cell counts; transfusion requirements; cellular composition of the bone marrow (% marrow blasts); and, markers of differentiation.

5 INVESTIGATIONAL PLAN

5.1 Overview

Note: 'Sub-cohort' (generally) refers to different treatment arms within the dose-finding Cohort.

This is a multi-center, open-label, multiple ascending dose- and duration-finding study assessing the safety, pharmacokinetics and pharmacodynamics of IMG-7289, with and without ATRA, in patients with advanced myeloid malignancies. Following their consent, patients will undergo Screening to confirm eligibility. A sufficient number of patients will be screened to enroll and treat approximately 40 patients with high risk AML/MDS. Screening may commence up to 28 days prior to the start of IMG-7289 treatment on Day 1. Patients meeting all applicable Inclusion and no Exclusion Criteria will be enrolled into the study and assigned to a Cohort. All patients will be unique; no patient will be allowed to be dosed in more than one cohort. Contingent on the number of prior DLTs within a cohort, non-completers of Cycle 1 will be replaced.

Non-clinical studies indicate that the maximal differentiation and cell killing of AML cells is a result of complete inhibition of the enzyme. The dose of IMG-7289 (free base) estimated to provide in

humans a plasma concentration sufficient to inhibit the LSD1 enzyme throughout the 24 hour dosing cycle has been designated the D_i . Non-clinical studies indicate that an oral dose resulting in a C_{min} unbound plasma concentration at 24 hours post-dose of between 1 and 2 ng/mL of the free base of IMG-7289 is sufficient to fully inhibit LSD1 during the dosing cycle and hence, arrest normal myeloid haematopoiesis in mouse, rat and dog. This concentration approximates the IMG-7289 concentration needed to inhibit LSD1 activity fifty percent (IC_{50}) *in vitro* as well as the IC_{50} for killing cultured AML cells (6-9 nM free base). Based on pharmacokinetic modeling, the IMG-7289 free base dose needed to achieve this concentration in humans at 24 hours is approximately 3 mg/kg. The non-clinical and modeling data may not be precise enough to accurately predict the pharmacokinetic parameters in humans. Accordingly, as a measure of precaution, a starting dose of 0.75 mg/kg QD representing the estimated $<IC_{10}$ for inhibiting human platelet production has been selected as the starting dose and designated the D_s .

The D_s of 0.75 mg/kg QD (free base) is likely to be below the D_i , the dose anticipated to achieve an unbound plasma concentration of drug across the dosing interval sufficient to inhibit normal myeloid haematopoiesis. If, as expected, normal myeloid haematopoiesis is not significantly affected at the D_s , then planned dose escalation in subsequent sub-cohorts above the D_s are intended to identify the D_i . Similarly, the D_i may not be the equivalent of the dose needed to achieve the desired PD effects on malignant cells in high risk AML/MDS patients, a dose designated the D_p ; the D_p , which will be determined by the DSMC, may be higher *or* lower than the D_i . NB: the D_p may vary based on the IMG-7289 dose, treatment regimen (i.e., IMG-7289 alone *versus* combination therapy) or dosing duration. If the anticipated PD responses are not demonstrated at the D_i , then titrations above or below the D_i are intended to identify the D_p . Any potential dose titrations will be made with appropriate consideration to safety.

The study consists of two phases in which IMG-7289 will be dosed with and without ATRA: the dose-finding phase, using multiple ascending doses of IMG-7289; and the duration-finding phase, during which multiple IMG-7289 durations may be assessed. During both phases, a Data Safety Monitoring Committee (DSMC) will convene to review safety parameters, pharmacodynamic markers and pharmacokinetic parameters to draw conclusions around the safety and pharmacodynamic effects of differing doses, treatment regimens and dosing durations. DSMC reviews are critical, as neither a new dose-finding sub-cohort, nor a duration-finding cohort may commence without DSMC review and recommendation to do so. Refer to Section 8 for details pertaining to DSMC reviews, DLT management, dose escalation/duration extension rules, and MTDs.

At least three patients will enroll in each cohort/sub-cohort, with a minimum of 3 patients per cohort/sub-cohort required to complete the entirety of Cycle 1 (i.e., the applicable IMG-7289 dosing and rest periods). Each dose-finding sub-cohort will include a sentinel patient to be dosed for 7 days, the safety of which will be determined by the DSMC before the remainder of the sub-cohort is treated; duration-finding cohorts will not include sentinel patients. Therefore, with the exception of a sentinel patient in each dose-finding sub-cohort, patients will be enrolled on a rolling basis. As there is no evidence in non-clinical studies of acute toxicity with IMG-7289, even at extremely high doses, it is believed that one sentinel patient for each dose-finding sub-cohort is sufficient to establish the acute safety of IMG-7289 dosed with and without ATRA. Since this study is not

investigating the effects of cytotoxic agents, enrolling patients on a rolling basis facilitates progression to later cohorts that could offer greater therapeutic benefit.

Patients will be treated with IMG-7289 in cycles, each cycle comprised of one IMG-7289 dosing period followed by one rest period. The number of initially allowed IMG-7289 cycles differs by cohort, as does the duration of IMG-7289 dosing. Patients may initially undergo four (Cohort 1), two (Cohort 3/3 χ) or one (Cohort 4/4 χ) IMG-7289 treatment cycles while on study to a total of approximately 28 days of IMG-7289 dosing. During the initially allowed IMG-7289 treatment cycles and regardless of the dosing duration, the rest period will remain at 7 days, unless assessment is made by the DSMC that either a specific patient or an entire cohort could benefit from an extended rest period. This decision could be taken if there is no clear indication of the restoration of normal haematopoiesis in the 7 day period or analysis of the IMG-7289 pharmacokinetic parameters in the earlier sub-cohorts suggest the rest period duration requires adjusting. As IMG-7289 treatment may lead to cytopenias, transfusions may be administered in accordance with standard institutional guidelines.

The initial dose-finding phase of the study will be used to establish and confirm the IMG-7289 D_1 and the D_p in patients, as well as to provide samples sufficient to establish the pharmacokinetic parameters of IMG-7289 at several dose levels, with and without ATRA. It is anticipated that dose escalation of IMG-7289 as well as IMG-7289 administered in combination with ATRA will proceed in sub-cohorts (i.e., Sub-cohort 1b, 1c, 1 χ , 1w) in accordance with Section 7.2.2.1, following DSMC reviews as detailed in Section 8.1 and the rules outlined in Section 8.2.2. (Note: Though not expected, contingencies are in place in the case that unacceptable toxicity is demonstrated at the D_s and sub-cohorts at lower doses are therefore required. Please refer to Section 7.2.2.2.) The IMG-7289 dosing duration and associated rest period will remain at 7 days dosing followed by a 7 day rest period throughout the entirety of the dose-finding phase (includes all sub-cohorts)*. Patients will be initially allowed to receive up to 4 cycles of IMG-7289, provided that IMG-7289 (with and without ATRA) continues to be tolerated.

Upon DSMC confirmation that no further dose-finding sub-cohorts are anticipated, and safety permitting (the DSMC must have determined it safe to extend the duration of IMG-7289 treatment), the duration-finding phase will commence. The duration-finding phase will be used to identify the safety and clinical effects of IMG-7289 treatment for durations longer than 7 days as well as provide samples sufficient to establish drug concentrations at steady state, with and without ATRA. Duration-finding cohorts will be dosed with IMG-7289 at the D_p (determined by the DSMC), with or without ATRA. The D_p may change as data from earlier sub-cohorts becomes available and different durations continue to be studied. The duration of dosing will be extended in cohorts in accordance with Section 7.2.2.3, following DSMC reviews as detailed in Section 8.1 and the rules outlined in Section 8.2.2; each dosing duration will be followed by a 7 day rest period*. Patients will be initially allowed to receive **2 cycles** of 14 days IMG-7289 dosing for Cohorts 3/3 χ , and **1 cycle** of 21 days IMG-7289 dosing for Cohorts 4/4 χ ; each dosing duration will be followed by a 7 day rest period.*

*The duration of the rest period may be adjusted based on an assessment by the DSMC that either a specific patient or an entire cohort could benefit from an extended rest period. This decision could be taken if there is no clear indication of the restoration of normal haematopoiesis in the 7 day period or analysis of the

pharmacokinetic parameters in earlier cohorts (or sub-cohorts) suggest the rest period duration requires adjusting. Investigators will be notified of any such change.

Importantly, if the DSMC determines a specific dose, treatment regimen or dosing duration is associated with greater therapeutic benefit, patients who have *fully completed* their initially allowed cycles and are receiving a different dose, treatment regimen (i.e., IMG-7289 alone *versus* combination therapy) or dosing duration will be transitioned to the more optimal dose, treatment regimen or dosing duration at the start of their next cycle. Such transition may occur more than once, as different doses, treatment regimens and dosing durations continue to be evaluated.

Throughout all phases of the study, if it appears that either a maximally tolerated dose (MTD) or maximally tolerated duration (MTD_u) is reached (see Section 8.2.3), the DSMC will convene to evaluate further dose escalation, combination therapy and/or extended dosing duration.

Upon completion of the number of initially allowed IMG-7289 cycles per cohort, patients deriving clinical benefit and safely tolerating IMG-7289, as determined by the Principal Investigator, may continue to receive IMG-7289 with additional dose titration, treatment regimen and dosing duration changes occurring in consultation with the Medical Monitor until disease progression or unacceptable toxicity ensues. During the additional cycle period, the rest period may be extended from the 7 day standard to a maximum of 56 days but only after: 1) the patient has received a minimum of 28 IMG-7289 doses; and, 2) consultation with or recommendation by the DSMC. Such recommendation may be made for a variety of reasons including evidence of tumour reduction, marked hypocellularity in the marrow consistent with myelosuppression, or to enable the return of normal haematopoiesis. For protocol purposes, a rest period extending beyond the 7 day standard will be referred to as the extended rest period (see Section 9.10).

Patients who either fail to demonstrate stable disease, demonstrate progressive disease after achieving partial remission (PR) or stable disease, or relapse after achieving complete remission (CR), CR with incomplete recovery (CRi), or PR (see **Table 14** and **Table 15**) are the equivalent of treatment failures, and will discontinue study drug and enter the follow-up period.

Patients will be followed closely for both Adverse Events (AEs) and signs of toxicity by frequent monitoring of clinical signs and symptoms and by blood and urine analyses both during the IMG-7289 treatment period and the rest period. Pharmacodynamic effects will also be closely monitored by frequent haematology assessments of peripheral blood and bone marrow aspirates, as required.

All patients will undergo End-of-Treatment (EOT), pre-End of Study (pre-EOS), and End-of-Study (EOS) visits approximately 7, 14, and 28 days, respectively, after last Cycle last dose.

A detailed description by-cohort, by-cycle, of assessments to be performed is provided in Section 9. Additionally, a by-cohort schema of assessments is included in Section 16.1, Schedule of Assessments.

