6.4 Replacement of dropouts

A minimum of 3 patients per cohort/sub-cohort are required to complete the entirety of Cycle 1 (including the applicable treatment and rest periods). Contingent on the number of prior DLTs within a cohort/sub-cohort, non-completers of Cycle 1 will be replaced to ensure a minimum of 3 patients complete Cycle 1 of each cohort/sub-cohort.

CC

CCI

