If the DSMC determines combination therapy should proceed, then additional sub-cohorts will commence.

Sub-cohort 1w: Dosing will begin on Day 1 with IMG-7289 (dose to be determined by the DSMC) dosed for 7 days on followed by 7 days off, in combination with ATRA 45 mg/m² per day dosed for 21 days[§] on followed by 7 days off.

[§]Patient's enrolled in Sub-cohort 1χ will continue their current treatment regimen until completion of their initially allowed treatment cycles and pending DSMC review of the sentinel patient in Sub-cohort 1w, after which transition to the new (21 day ATRA) regimen may occur at the start of the next cycle.

If the DSMC determines that combination therapy offers greater therapeutic benefit as compared to single agent IMG-7289 therapy, then patients who have fully completed their initially allowed IMG-7289 treatment cycles and are receiving a different treatment regimen (i.e., IMG-7289 alone) will be transitioned to combination therapy at the start of their next cycle.

The table below summarizes the IMG-7289 in combination component of the dose-finding phase by sub-cohort, dose, dosing duration, rest period, and number of initially allowed IMG-7289 cycles.

Table 2: Combination Therapy Component of the Dose-finding Cohort

Sub-cohort	IMG-7289 Dose (free base)	IMG-7289 Cycle		No. of Initial IMG-7289 Cycles**
		Dosing Duration	Rest Period*	
1 χ	TBD [¥]	7 days on	7 days off	4
	Administered in combination with			
	ATRA [§] 45 mg/m ² /d for 7 days [§] on followed by 7 days off			
1w [§]	TBD [¥]	7 days on	7 days off	4
	Administered in combination with			
	ATRA [§] 45 mg/m ² /d for 21 days on followed by 7 days off			

*The duration of the rest period may be adjusted based on an assessment by the DSMC that either a specific patient or an entire cohort could benefit from an extended rest period. This decision could be taken if there is no clear indication of the restoration of normal haematopoiesis in the 7 day period or analysis of the pharmacokinetic parameters in the earlier sub-cohorts suggest the rest period duration requires adjusting; for example, if the half-life of IMG-7289 is unexpectedly long. Investigators will be notified of any such change.

**Additional cycles may be allowed, contingent on clinical benefit/patient response.

[¥]The IMG-7289 dose for administration with ATRA will be determined by the DSMC based on ongoing review of safety and pharmacodynamic data.

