DSMC reviews during the IMG-7289 in combination with ATRA component of the dose-finding phase are detailed below.

Combination therapy (see Section 7.2.2.1) will proceed in sub-cohorts (i.e., Sub-cohort 1w, 1v, etc.) provided that:

1. A minimum of 3 patients from the previous sub-cohort have completed Cycle 1, both the applicable dosing and rest periods
2. The number of patients who experience DLT is within the guidelines (Section 8.2.2)
3. DSMC review of the previous sub-cohort has determined that:
 - a. The doses administered in combination appear safe
 - b. Further combination therapy is appropriate

Upon DSMC confirmation that no further dose-finding sub-cohorts are anticipated, the DSMC will also make a determination of whether it is safe to extend the dosing duration, to determine whether longer durations are associated with greater therapeutic benefit. The study will then progress to assess the effect of IMG-7289 dosing duration.

DSMC reviews during the duration-finding phase are detailed below.

During the duration-finding phase, the DSMC will assess whether the longer duration of IMG-7289 dosing, with and without ATRA, at the D_p is safe and associated with greater therapeutic benefit using a combination of PD and PK markers. Each duration cohort will be separated by approximately one week to allow for completion and analysis of appropriate safety assessments required for provision to the DSMC.

There are two potential duration-extension pathways for the duration-finding cohorts: duration extension with IMG-7289 alone, or IMG-7289 administered in combination with ATRA. Therefore, prior to opening a duration-finding cohort, the DSMC will assess the safety and pharmacodynamic effects of the earlier sub-cohorts, and reach consensus on:

1. Whether it appears safe to extend the duration of IMG-7289 dosing
2. Whether there appears to be greater therapeutic benefit with IMG-7289 dosed in combination with ATRA.

Based on the above assessments, one of the duration-finding cohorts will commence.

The duration of dosing (see Section 7.2.2.3) will be extended in subsequent cohorts provided that:

1. A minimum of 3 patients in the previous cohort have completed Cycle 1, both the applicable dosing and rest periods
2. The number of patients who experience DLT is within the guidelines (see Section 8.2.2)
3. DSMC review of the previous cohort has determined that:
 - a. The duration of dosing appears safe
 - b. Further duration extension is appropriate

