The intended dosing plan for high risk AML/MDS patients is predicated on the supposition that LSD1 must be maximally inhibited to achieve the greatest therapeutic benefit. The concentrations of LSD1 inhibitors such as IMG-7289 (free base) used to achieve maximal effects on growth, differentiation and apoptosis *in vitro* with primary patient-derived AML cells as well as AML cell lines are similar to concentrations that *in vivo* inhibit red cell, platelet and granulocyte production. It is therefore expected that high risk AML/MDS patients will require treatment at doses sufficient to induce profound thrombocytopenia and neutropenia. These drug-induced but reversible cytopenias can be managed clinically as needed with platelet and red cell transfusions as well as broad-spectrum antibiotics in the case of febrile neutropenia, as are already standard practices in the routine management of AML/MDS patients receiving intensive SOC chemotherapy.

The effects of IMG-7289 on normal myeloid haematopoiesis observed in non-clinical studies are expected in humans; these are pharmacodynamic effects of LSD1 inhibition by IMG-7289, thus are not regarded as adverse. These events, with the exceptions noted below, will not be considered DLTs.

Dose Limiting Toxicity (DLT): DLT is defined as any one of the following AEs that occurs during the first cycle of therapy and is considered by the Investigator to be possibly, probably or definitely related to IMG-7289.

- A clinically significant bleeding event;
- Any Grade 4 or 5 non-haematologic adverse event;

- Any Grade 3 non-haematologic adverse event with failure to recover to Grade 1 within 7 days of drug cessation, with the following exceptions:
 - ≥ Grade 3 nausea, vomiting or diarrhoea that responds to standard medical care
 - ≥ Grade 3 aesthenia lasting less than 14 days
- Any Grade 3 electrolyte abnormality unrelated to the underlying malignancy and persisting greater than 24 hours.

Patients who experience a dose limiting toxicity (DLT) will have their dose adjusted downward if the Medical Monitor and Principal Investigator deem it safe for the patient to continue on IMG-7289. To ensure a minimum of 3 Cycle 1 completers, and contingent on the number of prior DLTs within the sub-cohort/cohort, such patients may be replaced.

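### In Sub-cohort 1w the DLT and completer window closes at Day 14 of a 21-day ATRA course, so IMG-7289-related events starting in the third ATRA week cannot enter the 2-of-3 count or the MTD definition

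*Protocol*

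**What the plan says.** **Cycle length.** Protocol 5.1 builds a cycle from one IMG-7289 dosing period and one rest period. In the dose-finding phase these "will remain at 7 days dosing followed by a 7 day rest period throughout the entirety of the dose-finding phase (includes all sub-cohorts". Table 2 repeats 7 on and 7 off for 1w.

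**Completers.** Section 5.1 requires at least 3 patients per sub-cohort "required to complete the entirety of Cycle 1 (i.e., the applicable IMG-7289 dosing and rest periods". Section 6.4 agrees: "A minimum of 3 patients per cohort/sub-cohort are required to complete the entirety of Cycle 1 (including the applicable treatment and rest periods". Section 8.1 makes the next combination sub-cohort conditional on the same event: "A minimum of 3 patients from the previous sub-cohort have completed Cycle 1, both the applicable dosing and rest periods".

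**DLT window.** Section 8.2.1 defines a DLT as "any one of the following AEs that occurs during the first cycle of therapy and is considered by the Investigator" as at least possibly related to IMG-7289. Section 8.2.3 applies the resulting MTD definition (fewer than 2 of 3 patients with a DLT) to combination sub-cohorts.

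**ATRA in 1w.** Section 7.2.2.1 gives ATRA "for 21 days[§] on followed by 7 days off".

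**Sentinel.** Section 5.1: "Each dose-finding sub-cohort will include a sentinel patient to be dosed for 7 days", after which the DSMC decides whether the rest of the sub-cohort may be treated. In 7.2.2.1, 1χ patients finish their initial cycles on their own regimen, "pending DSMC review of the sentinel patient in Sub-cohort 1w, after which transition to the new (21 day ATRA) regimen may occur".

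**The concern.** The regimen under test in 1w is IMG-7289 plus three continuous weeks of ATRA. The rule that decides whether it is tolerated looks only at the first two weeks. Section 3.7 explains that ATRA was lengthened to 21 days because the IMG-7289 half-life proved to be 4-5 days. No readable text lengthens the toxicity window to match. The safety argument in 3.7 compares the ATRA exposure with APL practice; it does not address ATRA given with IMG-7289.

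Two decisions are affected. The 2-of-3 rule can pass 1w, and 1w can be counted as at or below the MTD, without one full ATRA course inside the counting window. And the stated safety condition for moving 1χ patients to 21-day ATRA is a review of a patient dosed for 7 days, when the two schedules are still identical.

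**Working it through.** **1. Check the cycle length against the plan's own figures.** The synopsis allows up to 28 days of screening and 28 days of follow-up after the last dose. Participation = (28 + days to last dose + 28) / 7.

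- Cohort 1: days to last dose = 3×14 + 7 = 49; (28 + 49 + 28)/7 = 105/7 = 15 weeks.
- Cohorts 3/3χ: 21 + 14 = 35; 91/7 = 13 weeks.
- Cohorts 4/4χ: 21; 77/7 = 11 weeks.

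All three match the stated 15, 13 and 11 weeks. Section 10 uses about 15 weeks for every Cohort 1 sub-cohort. A 28-day cycle in 1w would give 3×28 + 7 = 91 days to last dose and (28 + 91 + 28)/7 = 21 weeks. The 1w cycle is therefore 14 days.

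**2. Map ATRA days to IMG-7289 cycles.** With 14-day cycles, ATRA Day 14 is Cycle 1 Day 14, Day 15 is Cycle 2 Day 1, and Day 21 is Cycle 2 Day 7. The schedule of assessments agrees. In 16.1.3, patients on 21-day ATRA continue through the IMG-7289 rest period in Cycle 3 but not in Cycles 2 or 4, and they return the previous cycle's ATRA in Cycles 2 and 4. In 16.1.8 the pattern alternates by cycle.

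**3. Compare the combination cohorts (Tables 2 and 4).**

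| Cohort | Cycle 1 length | First ATRA course | ATRA days inside Cycle 1 |
|---|---|---|---|
| 1χ | 14 days | 7 days | 7 of 7 |
| 1w | 14 days | 21 days | 14 of 21 (67%) |
| 3χ | 21 days | 14 days | 14 of 14 |
| 4χ | 28 days | 21 days | 21 of 21 |

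Only 1w leaves part of its first course outside. Cohort 4χ gives the same 21 ATRA days wholly inside its window.

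**4. Illustrate the effect on the count rule.** The documents give no DLT rate or onset pattern, so both are assumed. Let p be the true 21-day probability of a DLT-type event, and f the share of the cumulative hazard falling by Day 14. Then q = 1 − (1 − p)^f, and P(0 or 1 counted DLT in 3) = (1 − q)³ + 3q(1 − q)².

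| p | f = 1 | f = 0.9 | f = 0.8 | f = 2/3 (constant hazard) |
|---|---|---|---|---|
| 0.40 | 0.65 | 0.69 | 0.74 | 0.80 |
| 0.50 | 0.50 | 0.55 | 0.61 | 0.69 |
| 0.60 | 0.35 | 0.41 | 0.47 | 0.56 |

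Example: p = 0.50 and f = 2/3 give q = 1 − 0.5^(2/3) = 0.370, and 0.630³ + 3×0.370×0.630² = 0.69.

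**5. Sentinel timing.** 1w first differs from 1χ on Day 8, after the sentinel's 7 days. To see whether this would produce an early switch, take the fastest enrolment:

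- The first 1χ patient starts on Day 1 and the other two on Day 8; these two complete Cycle 1 on Day 8 + 13 = 21.
- The 1w sentinel starts on Day 22.
- The first 1χ patient finishes four cycles on Day 4×14 = 56. By then the 1w sentinel has completed 56 − 21 = 35 days.

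If instead the third 1χ patient starts on Day s, the sentinel has completed 56 − (s + 13) = 43 − s days by Day 56. This is below 21 only if s exceeds 22, that is, if the third 1χ patient starts more than 21 days after the first (or review takes equivalently longer).

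**The case against.** **The DSMC is not bound by the count.** It must separately find that the combination appears safe (8.1). It may stop without 2 DLTs (8.2.2), and its duties run to study end. Adverse events and haematology are collected through Cycle 2 (16.1.3). This stands: a reader might infer that toxicity in the third week is ignored, and the documents do not support that. Discretion does not, however, alter the DLT definition or the MTD count.

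**Some of Days 15-21 will have been seen.** Under fastest enrolment the sentinel reaches Day 21 when the other two reach Day 14, so 21 + 14 + 14 = 49 of 63 ATRA patient-days have elapsed, and slower enrolment adds more. Section 8.1 also separates dose sub-cohorts by about a week. That sentence sits under the IMG-7289-alone reviews; if it also covers 1w, all 63 days pass before the next sub-cohort is dosed. Only 3×14 = 42 of the 63 can yield a counted DLT in either case.

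**A Cycle 1 DLT window is ordinary.** A reader might infer that 1w is special because a second IMG-7289 course on residual drug falls outside the window. That is equally true of 1χ and of 1a-1e, which share the IMG-7289 schedule. The ATRA days that 1w adds over 1χ in the first three weeks, Days 8-14, are inside the window. What is particular to 1w is that the Day 15-21 co-dosing follows unbroken ATRA.

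**ATRA toxicity alone is never a DLT.** Relatedness to IMG-7289 is required on any day, and 8.3 handles ATRA toxicity separately. The point is confined to events at least possibly related to IMG-7289.

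**ATRA exposure falls.** Section 3.4 cites AUC reductions of as much as 90% after about a week. This makes constant hazard a pessimistic case.

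**The sentinel is meant for acute safety,** and step 5 shows that an early 1χ switch is unlikely. A reader might infer that patients will in practice be moved on 7 days of evidence; normal timing argues against it.

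**Some text is not visible.** The body of 8.2.2 and Section 9 are blacked out, and the Data Safety Monitoring Plan is not supplied. The readable DLT definition and the synopsis rules contain no exception for 1w.

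**Conclusion.** The gap is real and narrow. As written, the counting window in 1w covers 14 of 21 days of the first ATRA course, and an IMG-7289-related event starting on Days 15-21 cannot enter the 2-of-3 rule or the MTD definition. That much follows from the text and schedule, without assumptions.

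The probabilities in step 4 describe the count rule alone, on assumed rates and timing. At a 50% rate the chance of passing the count rises from 0.50 to between 0.55 and 0.69. They should not be read as the chance that 1w would be cleared, because the DSMC's own judgement is a second gate.

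The sentinel condition for switching 1χ patients is weak as worded, since it can be met before the schedules differ, but an actual early switch needs slow 1χ enrolment or review. Overall this is a cheap improvement to the safety rule, not a failure of safety oversight.

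**What to change.** In 8.2.1, 8.1 and 6.4, with the matching text in the synopsis and 5.1, add one rule for 1w and any later sub-cohort whose ATRA course outlasts the IMG-7289 cycle:

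- The DLT and completion window ends no earlier than ATRA Day 21. A patient counts among the 3 after a DLT in that window or on completing it; others are replaced under the existing provisions.
- The 1w sentinel must have completed 21 days of ATRA, with DSMC review, before any 1χ patient switches. Keep the 7-day acute check for opening the rest of 1w.
- Report the 1w DLT count at both Day 14 and Day 21.

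**Cost.** This is a wording change; the Cycle 2 visits already exist. Each 1w review comes about 21 − 14 = 7 days later. If 10% of patients left during the added week (assumed), replacements would be 3/0.9 − 3 = 0.33 per 3 completers; at 20%, 3/0.8 − 3 = 0.75. The longer window takes in a second IMG-7289 dosing week, so the Day 21 count is not strictly comparable with 1χ; the Day 14 count keeps that comparison. A full 28-day window would add 14 days instead of 7 and is debatable, as is holding all 1w enrolment until the sentinel reaches Day 21.
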